- j. For each SAE, it should be evaluated whether it concerns an SSE. If it concerns an SSE, the SAE should be documented as such in the eCRF and the necessary actions should be taken (see footnote h). In case hospitalization occurs, it should be evaluated whether the hospitalization is related to the high-risk metastase(s) and this information should be documented in the eCRF. Note that only (S)AE related to the bone metastatic disease or related to radiotherapy (only applicable for arm B) must be reported in the eCRF and that all SSE need to be registered in both study arms, including an SSE in a bone metastasis that was not previously included in the study (only applicable for arm B). An exception are SSE's in bone metastases that were already treated with surgery or RT before study participation.
- k. In case of discontinuation of a subject's participation without withdrawal of consent, only survival data will be collected at the remaining follow-up timepoints (i.e. 1m, 3m, 6m, 12m, 18m and 24m after randomization date) and the occurrence of an SSE will be registered in the eCRF if it occurs within 24m after the randomization date.
- l. Patients in the upfront RT arm developing new minimally symptomatic or asymptomatic high-risk bone metastases during study participation are strongly advised to further be treated with preventive RT. Details concerning the characteristics of these new high-risk metastases as well as details regarding the preventive RT must be captured in the eCRF.

Clinical Trials Oncology

Ref.Nr.: P.01-S.23

Versie: 6.0

Administrative structure

Study responsible physician:	[name] Iridium Netwerk Department of Radiation Oncology [name]
Project managers:	Clinical Trials Office (CTO), Oncologisch Centrum ZAS [contact], [contact] [contact] www.clinicaltrials oncology.be
Sponsor	ZAS vzw, [name] [contact] www.zas.be

1. Background & Rationale

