2. Study objectives and endpoints

The primary and secondary objectives and endpoints of the study are presented in Table 2.

Table 2: Objectives and endpoints for the Hermes trial

Objectives	Endpoints
Primary	
To assess whether early preventive radiation of the high-risk asymptomatic or minimally symptomatic bone metastases in patients with metastatic cancer can decrease the number of SSEs*.	
 Time to a symptomatic skeletal related event (SSE) in any bone metastasis or death due to any cause.
Secondary	

 To evaluate the need for hospitalization related to the high-risk bone metastase(s) To assess overall survival (OS) To evaluate quality of life (QoL) 	
 The number of hospitalizations related to the high-risk bone metastases will be compared between systemic therapy/observation (arm A) and upfront RT (arm B) from date of study randomization to last follow-up visit (24m after randomization date), date of death of any cause or early end of participation in the study due to other reasons Overall survival will be assessed from time of study randomization to date of death of any cause or last follow-up visit (24m after randomization date) Quality of life will be compared between systemic therapy/observation (arm A) and upfront RT (arm B),

 To evaluate acute and late toxicity 	
using the EORTC QLQ-C15-PAL questionnaire (see appendix 2) and the EuroQol Group EQ-5D-5L questionnaire (see appendix 3)
 
 Adverse events in both study arms will be evaluated using the National Cancer Institute Common Terminology Criteria for Adverse Events (NCI-CTCAE) v5.0 (see appendix 4) from the time of ICF signing to last follow-up visit (24m after randomization date), date of death of any cause or early end of participation in the study due to other reasons. Only adverse events that are related to the bone metastatic disease or related to the radiotherapy (only for patients in arm B) will be reported in the eCRF.
---	--

*SSEs are defined as:

- symptomatic pathological fracture
- spinal cord compression leading to neurological deficit or pain
- Indication for palliative radiotherapy (for bone pain, cord compression or (impending) fracture)
- Indication for orthopedic surgery (for bone pain, cord compression or (impending) fracture)

3. Overall study design.

[figure not shown]

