7.1.4 Karnofsky Performance Score (KPS)

The KPS should be documented in the subject's medical record or study source documentation at applicable visits. A copy of the document is included in Appendix 5 (Karnofsky Performance Score Assessment) for reference.

7.1.5 High-risk bone metastase(s) characteristics: (localization, high-risk definition, number of metastases enrolled)

Based on imaging (CT, MRI or PET-CT), the characteristics of the high-risk bone metastasis(es) that is (are) asymptomatic or minimally symptomatic will be determined and captured in the eCRF, including the total number of bone metastases, the location of the high-risk bone metastases (high-risk definition) and the number of metastases enrolled.

High-risk is defined as follows:

- o Bulky site of disease in bone (diameter ≥ 2 cm)
- o Disease involving the hip (acetabulum, femoral head, femoral neck), shoulder (acromion, glenoid, humeral head), or sacroiliac joints
- o Disease in long bones with cortical involvement of $>1/3$ in proportion to the diameter of the bone (humerus, radius, ulna, clavicle, femur, tibia, fibula, metacarpals, phalanges)
- o Disease in vertebrae of the junctional spine (C1-2, C7- T1, T12-L1, L5-S1) and/or disease with posterior element involvement or epidural extension (Bilsky epidural compression score 1a-3; see appendix 7) [Bilsky et al]

Furthermore, whether metastases on other locations than the bone are present should be documented in the eCRF.

Images up to 12 weeks old at the time of randomization are allowed. If not available, screening will take place at the time repeat imaging will be performed according to the standard of care guidelines.

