7.2 Efficacy Evaluations

- Comparison of the number of SSE's in both study arms. SSEs are defined as:
 - symptomatic pathological fracture
 - spinal cord compression leading to neurological deficit or pain
 - Indication for palliative radiotherapy (for bone pain, cord compression or (impending) fracture)
 - Indication for orthopedic surgery (for bone pain, cord compression or (impending) fracture)

All SSE's will be recorded in both study arms. Patients in the upfront RT arm may develop an SSE in a bone metastasis that was not previously included in the study, which also needs to be registered. An exception are SSE's in bone metastases that were already treated with surgery or RT before study participation

Patients in the upfront RT arm developing new minimally symptomatic or asymptomatic high-risk bone metastases during study participation are strongly advised to further be treated with preventive RT. Details concerning the characteristics of these new high-risk metastases as well as details regarding the preventive RT must be captured in the eCRF.

- Comparison of the number of **hospitalizations** related to the high-risk bone metastasis(es) between observation/systemic therapy and upfront RT plus observation/systemic therapy
- **Overall survival:** from time of study randomization to date of death of any cause or last follow-up visit (24m after randomization date)
- To compare **quality of life** between observational arm (arm A) and upfront RT arm (arm B), using the EORTC QLQ-C15-PAL form and the EuroQol Group EQ-5D-5L form

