9.3 Statistical methods for analysing primary and secondary outcomes

Primary objective:

The primary endpoint (SSE-free survival) is a composite endpoint of SSEs and death (death before SSE is part of the endpoint, not a competing risk). The primary endpoint is time until the occurrence of SSE in any bone metastasis or death from the date of randomization whichever occurs first. Data suggest that the median SSE-free survival is around 10.4 months. With a HR of 0.5, we hypothesize that the median SSE-free survival will be 20.8 months.

A proportion of patients will have multiple high-risk bone lesions. Pain will be reported lesion-based, however the SSE-free survival remains patient-based as this is more clinically relevant.

Secondary objectives

- The number of **hospitalizations** related to the high-risk metastase(s) will be compared between systemic therapy / observation (arm A) and upfront RT plus systemic therapy / observation (arm B) from date of study randomization to last follow-up visit (24m after randomization date), date of death of any cause or early end of participation in the study due to other reasons
- **Overall survival** will be assessed from time of study randomization to date of death of any cause or last follow-up visit (24m after randomization date)
- **Quality of life** will be compared between systemic therapy / observation (arm A) and upfront RT plus systemic therapy / observation (arm B), using the EORTC QLQ-C15-PAL questionnaire (see appendix 2) and the EuroQol Group EQ-5D-5L questionnaire (see appendix 3)
- **Adverse events** in both study arms will be evaluated using the National Cancer Institute Common Terminology Criteria for Adverse Events (NCI-CTCAE) v5.0 (see appendix 4) from the time of ICF signing to last follow-up visit (24m after randomization date), date of death of any cause or early end of participation in the study due to other reasons. Only adverse events that are related to the bone metastatic disease or related to the radiotherapy (only for patients in arm B) will be reported in the eCRF.

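### Footnote j of Table 1 contradicts itself and the primary endpoint: it ties SSEs in non-study bone lesions to arm B, although the endpoint counts them in both arms

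*Protocol*

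**What the plan says.** The endpoint has the same definition wherever it is given. Section 9.3: "The primary endpoint is time until the occurrence of SSE in any bone metastasis or death from the date of randomization". Table 2 in section 2 and the synopsis agree: "in any bone metastasis or death due to any cause". None of the three limits it by arm.

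The registration instructions are less consistent:

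- **Table 1, footnote j**, first clause: "all SSE need to be registered in both study arms". The same sentence continues "including an SSE in a bone metastasis that was not previously included in the study (only applicable for arm B" and closes the parenthesis.
- **Section 7.2**, first sentence on recording: "All SSE's will be recorded in both study arms". The next sentence reads "Patients in the upfront RT arm may develop an SSE in a bone metastasis that was not previously included in the study" and asks for such an event to be registered. Arm A is not mentioned.
- **Both places** give one exception, for lesions treated with surgery or RT before study participation. It applies to both arms.

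Section 7.1.5 has the lesions characterised at screening, before randomization. It captures the total number of bone metastases as well as "the location of the high-risk bone metastases (high-risk definition) and the number of metastases enrolled". Enrolled and non-enrolled bone lesions are therefore distinguished in both arms.

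**The concern.** Footnote j uses the same arm B parenthesis twice in one sentence. The first use follows AEs related to radiotherapy and is a real restriction, since only arm B receives upfront RT. A site will naturally read the second use the same way: an SSE in a non-study lesion is registered if the patient is in arm B, and otherwise need not be. Section 7.2 does not remove the doubt, because its only example is an upfront RT patient.

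The restriction has no basis in the design. A bone lesion that was not enrolled, or that appears later, can cause an SSE in either arm.

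At stake is equal ascertainment of the primary endpoint. The trial is unblinded (section 5.2) and follow-up imaging is not standardised (section 6.1.3), so event capture depends on what sites register. An event that was never entered cannot be restored at the analysis stage. Missing events in arm A alone would make the control arm look better than it is.

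**Working it through.** **1. The protocol's own figures.** Inputs from sections 9.1, 9.3 and 5.2: HR 0.5, alpha 0.05, power 0.80, 2-year SSE-free survival 20% against 45%, control median 10.4 months, 1:1 allocation, 20% drop-out.

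- Events (Schoenfeld, two-sided): 4 × (1.960 + 0.842)² / (ln 0.5)² = 65.3. The protocol states 65. Sidedness is not stated; the one-sided formula gives 52 and Freedman's formula gives 71, so two-sided Schoenfeld is the version that reproduces.
- Patients: mean 24-month event probability (0.80 + 0.55)/2 = 0.675; 65/0.675 = 96.3, so 96; 96/0.80 = 120.
- Survival: exp(−ln 2 × 24/10.4) = 20.2%, and 44.9% at HR 0.5.
- Power with 65 events: Φ(√65/2 × 0.693 − 1.960) = Φ(0.834) = 0.798.

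The design figures stand, and the wording problem does not touch them.

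**2. Effect if the parenthesis is followed.** Let f be the share of the arm A event hazard that comes from SSEs in non-study lesions and is not registered. The protocol gives no value, so f is an assumption. With constant hazards, apparent HR = true HR/(1 − f), and power at 65 events = Φ(√65/2 × |ln HR| − 1.960).

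| f (assumed) | Apparent HR, true 0.50 | Power at 65 events | Apparent HR, true 1.00 |
|---|---|---|---|
| 0 | 0.500 | 0.798 | 1.00 |
| 5% | 0.526 | 0.735 | 1.05 |
| 10% | 0.556 | 0.659 | 1.11 |

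With the events expected from 96 patients at 24 months instead of a fixed 65 (64.1 and 63.3), power is 0.729 and 0.647. The bias is against radiotherapy in every row with f above zero.

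**3. How large f could be.** Death is part of the endpoint, so SSEs are only part of the arm A hazard. The total is ln 2/10.4 = 0.0667 per month.

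- From Table 3 in section 5.1 (NRF-model), best class: median OS 64 weeks = 14.72 months, death hazard ln 2/14.72 = 0.0471. The remainder for all SSEs is 0.0196/0.0667 = 29%.
- From the phase II result in section 1, 29% SRE incidence at 1 year: −ln(0.71)/12 = 0.0285, and 0.0285/0.0667 = 43%. If the 29% is instead read as a cumulative incidence with death competing at this trial's rates, the share is 0.29/(1 − exp(−0.0667 × 12)) = 0.29/0.551 = 53%.

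On the 29% to 43% range, f = 5% means that 12% to 17% of arm A SSEs fall outside study lesions and go unregistered. For f = 10% it is 23% to 34%, for f = 20% 47% to 69%, and for f = 30% 70% to more than 100%. Even at a 53% share, f = 20% needs 38%.

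This is a rough check. The 64-week median has no defined upper confidence limit, SREs are broader than SSEs, and the 28-week median for two risk factors is shorter than the assumed 10.4-month SSE-free median.

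**The case against.** The strongest reply is that the protocol sets one rule, and one stray parenthesis does not change it. Most of this stands:

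- The endpoint definition does not differ by arm, and both footnote j and section 7.2 first require all SSEs in both arms.
- Footnote j is attached to the adverse-event row of Table 1. The general SSE instruction is footnote h, repeated in section 6.2, and it has no arm or lesion limit. Nor do footnote k and section 6.3.1, which keep SSE registration going after discontinuation.
- Amendment 2 gives its purpose as clarifying that SSEs at any bone metastasis are recorded in both arms, which shows the intent.
- The section 7.2 sentence can be read as an illustration. The parenthesis may only reflect the authors' thinking about irradiated and non-irradiated lesions in arm B.

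A reader might also infer that every patient has non-study bone lesions, because more than 3 metastases are required and at most 5 locations can be enrolled. The documents do not support this: the count in section 4.2 covers all metastases, not bone alone. The point needs only that arm A patients can have or develop such lesions.

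The reply does not remove the defect. A general rule followed by an explicit arm restriction leaves sites to decide which one governs, and for the primary endpoint they should not have to.

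**Conclusion.** The point holds as an internal contradiction in current text. Footnote j conflicts with its own first clause and with the endpoint definition in sections 2 and 9.3, and section 7.2 leaves the same asymmetry in place. If sites act on the parenthesis, arm A events are under-registered and the hazard ratio is biased against radiotherapy.

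Two stronger readings should be resisted. One is that the primary endpoint is defined by different rules in the two arms. It is not, and any bias depends on sites following the parenthesis over the other instructions. The other is that the trial could lose half its power or more. Shares of 20% or 30% would give apparent HRs of 0.63 and 0.71 and power at 65 events of 0.47 and 0.27. They require a very large part of all arm A SSEs to lie outside study lesions with every one missed, which the protocol's own survival and SRE figures make implausible.

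A fair illustration is a 5% to 10% loss of the arm A hazard: apparent HR 0.53 to 0.56 and power about 73% to 66%. It assumes constant proportional loss, exponential event times, two-sided alpha of 0.05 and 65 events. The true size is unknown and may be zero if sites already register every SSE.

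**What to change.** 1. In Table 1, footnote j, delete the second arm B parenthesis, the one after the clause on SSEs in non-study lesions. The first one, on AEs related to radiotherapy, stays.
2. In footnote j and section 7.2, state that an SSE at any bone metastasis, enrolled or not, is registered and counted for the primary endpoint in both arms, subject only to the existing exception for lesions treated before study participation. In section 7.2, let the sentence on non-study lesions refer to patients in either arm.
3. Check that no eCRF form, edit check or completion guide restricts this entry to arm B. If patients have already been randomized, query sites for arm A SSEs in non-study lesions that were not entered.

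The cost is a wording amendment, an eCRF check and possibly one round of queries. Sample size, visits and patient burden do not change.

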	
 o Disease involving the hip (acetabulum, femoral head, femoral neck), shoulder (acromion, glenoid, humeral head), or sacroiliac joints o Disease in long bones with cortical involvement of >1/3 in proportion to the diameter of the bone (humerus, radius, ulna, clavicle, femur, tibia, fibula, metacarpals, phalanges) o Disease in vertebrae of the junctional spine (C1-2, C7- T1, T12-L1, L5-S1) and/or disease with posterior element involvement or epidural extension (Bilsky epidural compression score 1a-3) [Bilsky et al]. The posterior elements of the spine consist of the pedicles, laminae, facets (articular processes), transverse processes, and the spinous process. 
 - Number of Risk Factors (NRF) prognostic score 0-2 (see section 5.1) - Age ≥ 18 years - Ability to provide informed consent (either by the patient or by a legally authorized representative) - A female participant is eligible to participate if she is not pregnant and one of the following conditions applies: Is not a woman of child bearing potential or A woman of child bearing potential must have a negative serum pregnancy test at screening (see Section 7.1.7) and must use a very effective method of birth control 
Exclusion criteria
 
 - Previous RT to the target treatment site(s) - NRF prognostic score 3 (see section 5.1) - Serious medical co-morbidities that preclude RT - Bone lesion complicated with a pathological fracture or impending pathologic fracture for which prophylactic stabilization is recommended, characterized by Mirels score of ≥9 [Mirels et al] (see appendix 8) - Spinal metastasis with SINS score >13 requiring upfront neurosurgical stabilization [Fourney et al]. - More than 5 high-risk asymptomatic or minimally symptomatic metastatic bone locations

Study objectives and endpoints:
	
Primary objective and endpoint:

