5.1 Description

Patients will be randomized (1:1) to receive either systemic therapy/observation (Arm A) or early RT plus systemic therapy / observation (Arm B).

Arm A:

The observational arm (Arm A) will include **observation or systemic therapy**, according to the treating physician's discretion. Systemic therapy may include continuation of the current systemic therapy or initiation of a new systemic therapy.

These patients will be able to receive palliative RT to progressed, painful lesions (an SSE) only at the time of symptom worsening (NRS > 2/10 or need for opioids) or determination of spinal cord compression with neurological symptoms or (high risk for) fracture requiring surgical intervention. Upfront preventive RT is not allowed.

Arm B:

The intervention in this study is **early, upfront radiation therapy** to asymptomatic or minimally symptomatic (defined as high-risk) bone metastases. Up to 5 high-risk asymptomatic or minimally symptomatic metastatic locations per patient are allowed.

The radiotherapy (RT) doses used will be in accordance with common practice palliative RT schedules. As such a single fraction of 8 Gy is considered for all patients, except for patients with a very good prognosis (NRF prognostic score 0-1) in which a higher dose will be used with SABR [Chow et al].

Table 3: Predictive model for estimation of median overall survival (OS): NRF-model [Chow et al].

Three variables:

- **Primary cancer type** -> risk factor: non breast/prostate/lung cancer
- **Site of metastases** -> risk factor: metastases other than bone
- **Karnofsky performance score (KPS)** -> risk factor: KPS ≤60

0-1 risk factors	median OS 64 weeks	95%CI: 37-undefined
2 risk factors	median OS 28 weeks	95% CI 22-34
3 risk factors	median OS 10 weeks	95% CI 8-13

Simulation:

All patients will be immobilized in a comfortable and stable position to irradiate the metastatic lesion(s). Support and/or immobilization devices will be used to increase patient comfort or to ensure set-up reproducibility. A planning CT scan will be acquired without intravenous contrast with <3mm CT slice thickness (1mm for SABR) encompassing the region of interest with sufficient margin for treatment planning, a typical scan length should extend at least 10 cm superior and inferior beyond the treatment field borders. The isocenter will be placed in the middle of the affected bone lesion.

Target volume definition:

1. *Conventional radiotherapy:*

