Appendix 8: Mirels score [Mirels et al]

Fracture		Score	
Site	Upper limb	1	
	Lower limb	2	
	Proximal femur (peri-trochanteric)	3	
Pain	Mild	1	
	Moderate	2	
	Functional (worse on use of limb)	3	
	Sclerotic (blastic, gain of bone)	1	
Lesion	Mixed (combination of sclerotic and lytic)	2	
	Lytic (loss of bone)	3	
Ratio of lesion to diameter of bone*	<1/3 diameter 1	1/3-2/3 2	>2/3 diameter 3
			
Total	8=15% fracture risk	/12	
	9=33% fracture risk		

*Permeative or "moth-eaten" lesions can be poorly defined, multiple in nature, or ragged in appearance, and can be difficult to accurately quantify using this system.³¹ Seek specialist radiology or orthopaedic input for aid in classifying lesions if required

- Score ≤ 7 = the probability of fracture (5%) is low and such a lesion may be treated conservatively
- Score 8 = the probability of fracture (15%) is intermediate, discussion with orthopedic surgeon is advised
- Score ≥ 9 = the probability of fracture (33% and more) warrants prophylactic fixation of the bone

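### Arm B's advice to irradiate new painless lesions has no upper fracture-risk limit, and no rule says whether the SSE list prevails when a lesion meets both

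*Protocol*

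**What the plan says.** **Advice in arm B.** Footnote l to the schedule of events, repeated in section 7.2, concerns new lesions in the upfront RT arm that cause little or no pain: "high-risk bone metastases during study participation are strongly advised to further be treated with preventive RT". It names no upper limit of fracture risk.

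**What counts as high-risk.** For long bones the definition sets a lower bound only: "Disease in long bones with cortical involvement of >1/3 in proportion to the diameter of the bone".

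**Limits at entry.** The exclusion criteria (synopsis and section 4.3) remove a patient with an "impending pathologic fracture for which prophylactic stabilization is recommended, characterized by Mirels score of ≥9", and a spinal lesion with SINS >13 that requires upfront stabilisation. Appendix 8 says of a Mirels score of 9 or more that "the probability of fracture (33% and more) warrants prophylactic fixation of the bone".

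**Arm A.** Section 5.1 forbids preventive RT. It allows palliative RT when symptoms worsen "or determination of spinal cord compression with neurological symptoms or (high risk for) fracture requiring surgical intervention".

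**Events.** The SSE list (synopsis, Table 2, section 7.2) is the same for both arms. Its third and fourth items are "Indication for palliative radiotherapy (for bone pain, cord compression or (impending) fracture") and "Indication for orthopedic surgery (for bone pain, cord compression or (impending) fracture"). Section 7.2 requires every SSE to be recorded in both arms, including SSEs in arm B lesions that were not part of the study at entry.

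**Data.** Footnote l asks for the characteristics of the new lesion and details of the RT. The only list of lesion characteristics in the protocol, in section 7.1.5 for screening, is "including the total number of bone metastases, the location of the high-risk bone metastases (high-risk definition) and the number of metastases enrolled". Footnote h asks for the reason for RT once an SSE has occurred.

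**The concern.** Two rules meet on the same arm B lesion. A new, painless lesion at the surgical threshold falls under the preventive-RT advice, which carries no event, and also under the SSE list, which makes it an event. The protocol does not say which applies.

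The choice exists in one arm only. In arm A there is no preventive RT, so RT given to such a lesion for fracture risk has only the SSE label. In arm B it has two possible labels, and section 5.2 states that blinding is not possible. The SSE item is an indication for surgery or palliative RT; if a site goes straight from footnote l to RT, that indication may never be written down. The endpoint affected is the primary one.

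There is also a safety side. For a lesion that Appendix 8 puts at a fracture probability of 33% or more, footnote l names RT and does not mention a surgical opinion.

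**Working it through.** **1. The plan's own figures.** Section 9.1 gives HR 0.5, alpha 0.05 (two-sided reproduces the figure), power 0.80, and 2-year SSE-free survival of 20% against 45%.
- Events (Schoenfeld): (1.960 + 0.842)² / (0.25 × (ln 0.5)²) = 65.35; the plan states 65.
- Patients: 65 / ((0.80 + 0.55)/2) = 96.3; stated 96. With 20% dropout, 96/0.8 = 120, as stated.
- Expected events at 24 months with 48 per arm: 48 × 0.80 + 48 × 0.55 = 38.4 + 26.4 = 64.8.

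Nothing in this point disputes these figures.

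**2. Can a new painless long-bone lesion reach Mirels 9?** Appendix 8 has no zero for pain, so painless or mild pain scores 1. Involvement above 1/3 scores 2 or 3. That gives 3 sites × 3 lesion types × 2 ratios = 18 profiles, of which 4 reach 9:
- peritrochanteric, lytic, 1/3–2/3: 3 + 1 + 3 + 2 = 9
- peritrochanteric, mixed, >2/3: 3 + 1 + 2 + 3 = 9
- peritrochanteric, lytic, >2/3: 3 + 1 + 3 + 3 = 10
- other lower limb, lytic, >2/3: 2 + 1 + 3 + 3 = 9

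A painless upper-limb lesion reaches at most 1 + 1 + 3 + 3 = 8.

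**3. Can a spinal lesion exceed SINS 13?** Taking NRS ≤2 to allow no pain (0) or occasional non-mechanical pain (1), Appendix 6 gives 4 × 2 × 3 × 3 × 4 × 3 = 864 profiles. Of these, 16 exceed 13: 4 with pain 0 and 12 with pain 1. All 16 need abnormal alignment, since with normal alignment the maximum is 3 + 1 + 2 + 0 + 3 + 3 = 12. Fifteen need subluxation or translation.

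The counts in steps 2 and 3 are score profiles, not patient frequencies.

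**4. One lesion, two arms.** Take the first profile in step 2, found after randomisation.
- Arm A: preventive RT is barred. RT is possible only as high risk of fracture requiring surgery, which the SSE list counts.
- Arm B: footnote l advises preventive RT, with no event attached. The SSE list also counts the lesion. No text ranks the two.

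For a new lesion below the surgical threshold, with no other indication for surgery or palliative RT, there is no conflict: arm A gives no RT, and RT in arm B is the tested strategy.

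**5. What one case would do (illustration).** Assumptions: exponential times, control hazard −ln(0.20)/24 = 0.067 per month, 48 per arm, 24 months. One arm B patient's first event goes unregistered and the next event, drawn at the same hazard, is still counted. At the design HR that is 1/26.4 = 3.8% of arm B events. Simulation with 20,000 trials per HR (6,000 for the HR estimate):

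| True HR | Estimated HR, without → with the miss | Chance of significance favouring arm B |
|---|---|---|
| 0.50 | 0.498 → 0.479 | 79.4% → 83.0% |
| 0.70 | 0.699 → 0.677 | 32.6% → 37.3% |
| 1.00 | 1.000 → 0.974 | 2.5% → 3.2% |

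If that patient never has a registered event, the estimates are 0.471, 0.664 and 0.949, and the chances 84.4%, 40.2% and 3.9%.

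**6. Range for an assumed rate.** If a fraction f of the arm B event hazard were lost with no true effect, the Schoenfeld approximation puts the one-sided error at 3.1% (f = 2%), 4.1% (5%), 6.6% (10%) and 15.7% (20%), against 2.5%. The documents give no value for f.

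**The case against.** The strongest reply is that the SSE list already settles the matter. It is identical in both arms, is triggered by an indication and not by the treatment given, and section 7.2 extends recording to new arm B lesions directly before it gives the preventive-RT advice. This stands. A reader might infer that the protocol makes the arm B lesion a non-event, or counts the endpoint differently by arm. The documents do not support that: as written, the lesion is an SSE in arm B too. What survives is narrower, namely that nothing says the list still applies when the lesion is handled as preventive RT.

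A reader might also infer that section 5.1 itself declares RT to the painless arm A lesion an SSE. The SSE label there is attached to progressed, painful lesions; the firm basis in arm A is the common list.

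Misfiling could run either way. Arm B preventive RT filed as palliative RT for impending fracture would add arm B events, and the SABR paragraph of section 5.1 shows that arm B RT and impending fracture can coincide. An arm A indication also depends on an unblinded physician writing it down. So a bias towards arm B is possible, not established.

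The eCRF is not shown and section 7.1.5 describes screening, so a Mirels or SINS field for new lesions may exist. The protocol text does not ask for one. Finally, the advice is not mandatory and fixation is not barred.

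**Conclusion.** The point holds as an overlap without a precedence rule. The preventive-RT advice reaches lesions the trial would refuse at entry. Those lesions also meet the SSE list, and only arm B offers an alternative, non-event label for RT to them.

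The size is unknown. Steps 2 and 3 show that such lesions can exist, not how often they occur. The simulated figures assume exactly one missed arm B event in the direction that favours arm B; any other single missed arm B event would have a similar effect. They show that a trial resting on about 65 events is sensitive to a handful of labels, and no total effect is claimed. The design figures of 65 events and 96 or 120 patients are unaffected. The correction should be made at the next amendment, because it is cheap, protects the primary endpoint and routes patients at high fracture risk to a surgical opinion.

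**What to change.** 1. In footnote l and section 7.2, limit the preventive-RT advice to new lesions below Mirels 9, at SINS 13 or less, and without an indication for stabilisation. Refer other new lesions for a surgical opinion.
2. Add that the SSE list applies in both arms regardless of preventive RT. A new lesion with Mirels ≥9, or with SINS >13 and an indication for stabilisation, is registered as an SSE in either arm on the date of that finding, whatever treatment is given. Word this as a sufficient and not a necessary criterion. Making the scores the definition of impending fracture would drop indicated surgery or RT below them, such as fixation of a painless Mirels 8 lesion, and would exclude every painless upper-limb lesion.
3. For every post-randomisation RT course to bone, in both arms, record the reason and, where one applies, the Mirels or SINS score.

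The cost is a wording amendment and two eCRF fields, with no extra patients or visits. One limit remains: follow-up imaging is discretionary (section 6.1.3), so the date on which a lesion is found may still differ between arms.
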